6.2.5 Subsequent antitumor therapy

Information on subsequent antitumor therapy needs to be collected and recorded on the eCRF/CRF for patients with progression of disease, including name, dose of the drug and duration of administration. Any information on the radiotherapy for progression of disease will also be collected, including the site of radiotherapy, Gy dose, start and end time.

7 Safety evaluation

7.1 Safety parameters and definition

7.1.1 Adverse event

Adverse event (AE) is defined as any adverse medical event which occurs during administration of study drug but not necessarily correlates with the therapy. Therefore, AE can be any adverse and unwanted signs (including abnormal laboratory findings), symptoms or diseases, which has temporary correlation with the medication but is not necessarily correlated with the medication.

In addition, AE also includes the complications caused by the intervention specified in the protocol, for example, invasive procedure including biopsy; and exacerbation of previous disease during the reporting period of AE, as considered by investigators (except tumor progression).

7.1.2 Serious adverse event

Serious adverse event (SAE) is defined as the adverse event meeting at least one of the following criteria:

- **death:** the adverse event leads to the subject's death, except that resulted from progression of disease;
- **life-threatening:** the investigator considers the subject is at the direct risk of death when experiencing the adverse event, rather than that it might lead to death on the premise that the event becomes more serious;
- **hospitalization or prolonged length of hospital stay:** the adverse event leads to hospitalization (not including seeing a doctor in emergency room or outpatient department), or occurs during the hospitalization and prolongs the length of hospital stay;
- **permanent or significant disability or loss of function:** the adverse event leads to the substantial impairment in the subject's activities of daily living (not including relatively minor events in terms of medical significance for loss of function, such as headache, nausea, vomiting, diarrhea, influenza and accidental trauma (eg., ankle sprain));
- **congenital deformity or birth defect:** the neonate (fetus) that is born or aborted by the female subject who has been exposed to the drug or the female partner of the male subject who has been exposed to the drug has congenital deformity or birth defect;

—**significant medical event:** the significant medical event might not cause threat to life, lead to death or hospitalization immediately, but would jeopardize the subject or require medical or surgical treatment to prevent occurrence of any of the above results (subject's death, life-threatening, hospitalization, prolonged length of hospital stay, permanent or significant disability or loss of function, congenital deformity).

7.1.3 Protocol-defined special events

The sponsor will keep persistent and close monitoring of the drug induced hepatic impairment although it is rare.

The serum chemistry should be closely monitored when the following conditions occur

- For subjects with normal transaminase at baseline who have more than 3 times elevation in ALT or AST of normal, or those with elevated transaminase at baseline who are found to have more than two times elevation in ALT or AST of baseline, serum chemistry should be closely monitored (ALT, AST, ALP and TBL) and the frequency of monitoring should be increased (2-3 times/week);
- For subjects with early symptoms of hepatic impairment before they are found having abnormal serum chemistry (eg., decreased appetite, nausea, vomiting, right upper abdominal discomfort, asthenia), serum chemistry test should be performed immediately, and the frequency of monitoring must be increased when the above abnormalities occur.

The following events are the protocol-defined special events:

- Subjects with normal hepatic function at baseline (ALT, AST and bilirubin within normal range) have AST and/or ALT elevated $>3\times\text{ULN}$ combined with serum total bilirubin elevated $>2\times\text{ULN}$ in the same blood sample collected.
- Subjects with elevated transaminase at baseline have AST and/or ALT elevated >2 times of baseline value combined with serum total bilirubin elevated $>2\times\text{ULN}$ in the same blood sample collected.

7.1.4 Progression of disease

In accordance with RECIST criteria 1.1, if the event is confirmed to be consistent with the expected progression pattern of the primary tumor, it should not be considered as AE. Hospitalization resulted only from progression of the disease should not be considered as SAE either. When the symptom could not be completely confirmed to be induced by the progression of disease, or is not consistent with the expected progression pattern of tumor, the relevant clinical symptom could be judged as AE.

The tumor related symptoms could be considered as AE only in the following conditions:

1. Newly occurring (ie., not present at baseline) and no clear correlation with the primary tumor and metastatic lesion, and/or

2. The investigator considers the exacerbation of tumor related symptom is directly correlated with the study drug.

When the event could not be determined to be induced only by the progression of disease, it should be considered as AE, and be reported as when SAE criteria are met.

7.2 Collection and evaluation of safety parameters

7.2.1 Definition of adverse event reporting period

Time Period	Reporting requirements
from the signature of informed consent to before administration of the first dose of study drug	Report SAE caused by the protocol-defined interventions (eg., invasive procedure including the biopsy, drug elution, no treatment preparation period)
from the first dose to within 30 days after the last dose of study drug	Report all the AE, including SAE except progression of disease, and all the death.
post-treatment period (30 days after discontinuation of the study drug)	Only report the SAE related with the study drug. Only report the death as SAE when it is considered to be related with the study drug.

7.2.2 Intensity assessment of adverse events

The intensity of all the AEs is graded in accordance with NCI criteria on common terminology for adverse event (CTCAE) version 4.0 and judged in 5 grades (Grade 1-5). The AE not listed in NCI CTCAE is judged via the following table.

Table 10. Criteria on judgment of the intensity of adverse event

CTC grade	Equal to	Definitions
1	Mild	discomfort observed but no impact on normal daily activities
2	Moderate	the discomfort adequate to reduce or affect daily activities: no use of treatment or medical intervention although they could improve patient's quality of life or relieve symptoms
3	Serious	inability to work or complete daily activities, treatment or medical intervention used to improve patient's quality of life or relieve symptom, delayed treatment would not bring patient in direct threat to life.
4	Life-threatening or disable	direct threat to life or resulting in permanent mental or physical impairment, inability to work or perform daily activities, treatment or medical intervention must be performed to maintain life.
5	Death	AE leading to death

Note: the severity and intensity of a adverse event are different. The intensity is defined as intense degree of adverse event (eg., mild, moderate or severe headache), however, the event itself might be of only minor clinical significance (e.g, severe headache), and could not be judged as SAE, unless it meets the criteria on SAE. Therefore, when reporting AE/SAE, the severity and intensity should be evaluated independently.

7.2.3 Drug-event relationship

The relationship between the study drug and adverse event, or its effect in the adverse

event could be judged using the following category and criteria:

- 1 unrelated: the adverse event is determined to be caused by other reasons (disease, environment, etc.) after careful medical judgment;
- 2 possibly unrelated: the adverse event is considered to be possibly unrelated with the study drug after careful medical judgment;
 - ◆ no temporal relationship between the occurrence of adverse event and use of the drug
 - ◆ The adverse event might be caused by other factors, including change in the course of disease, environment, or administration of other drugs.
 - ◆ The adverse event is unrelated with the known properties of the drug
 - ◆ No more occurrence or exacerbation of the adverse event after resumption of the administration
- 3 possibly related: (must have the first 2 items) the adverse event is considered to be possibly related with the study drug after careful medical judgment:
 - ◆ temporal relationship between the occurrence of adverse event and use of the drug
 - ◆ The occurrence of adverse event could not be excluded to be related with the course of disease, environment, toxicity or administration of other drugs.
 - ◆ The adverse event is consistent with the known properties of the drug.
- 4 Related: (must have the first 3 items) the adverse event is considered to be related with the study drug after careful medical judgment:
 - ◆ strong temporal relationship between the occurrence of adverse event and use of the drug
 - ◆ It could not be explained with the reasons of course of disease, environment, toxicity and administration of other drugs.
 - ◆ The adverse event is resolved or relieved after discontinuation of the drug or dose reduction, and recurred after resumption.
 - ◆ The adverse event is consistent with the known properties of the drug.

When reporting SAE, if the investigator judges it is possibly related, possibly unrelated or unrelated, the alternate reasons causing the SAE must be provided by the investigator.

7.3 *Recording and reporting of safety parameters*

7.3.1 Recording of adverse events.

During the reporting period of protocol-defined adverse events, the investigator is responsible for collecting all the AEs (including SAE) and recording them in the

CRF/eCRF. When recording the AE, the investigator should use proper and standard medical terms, and avoid spoken language and abbreviations.

7.3.2 Expedited reporting of serious adverse events

During the study, any serious adverse event regardless of the correlation with the study drug, serious adverse events judged by the principal investigator or assistant investigator, or the serious adverse events meeting the above criteria should be reported. The investigator should fax the completed serious adverse event report form to the food and drug administration in relevant province, autonomous regions and municipalities directly under the central government, China Food and Drug Administration, the sponsor and ethics committee within 24 hours after awareness of the serious adverse event. The clinical monitor shall review the written report within 5 business days after receiving it. The report should include demographics, history of medication, adverse events and concomitant medication. The investigator should record all the known information related with the event in the first report. The investigator should complete the follow-up report in the same time limit after acquisition of the follow-up information. If a non-serious AE progresses to serious, this and other relevant follow-up information must be reported within 24 hours as described above. Regardless of the correlation with the study drug, all the serious adverse events should be managed appropriately, until the investigator judges the patient has been recovered from the event or the event turns to be chronic or stable disease.

In order for the sponsor to obtain the safety data in a timely and comprehensive manner, the investigator should fill in the SAE report form in clinical study provided by Hutchison Medi Pharma (Shanghai) Co., Ltd., and fax it to the company within 24 hours, in addition to the serious adverse event report form from CFDA, for all the serious adverse events. If the subject is hospitalized for serious adverse event, the diagnostic and therapeutic information provided by the hospital should be faxed to Hutchison Medi Pharma (Shanghai) Co., Ltd. as soon as possible.

■ China Food and Drug Administration [contact]

■ Hutchison Medi Pharma (Shanghai) Co., Ltd. [contact]

7.3.3 Reporting of protocol-defined special events

The protocol-defined special events, regardless of SAE or the correlation with the study drug, need to be reported to Hutchison Medi Pharma (Shanghai) Co., Ltd.

- those meeting SAE criteria need to be reported in accordance with the expedited reporting procedure for serious adverse events (as shown in 7.3.2);
- those not meeting SAE criteria only need to complete the SAE report form in clinical study provided by Hutchison Medi Pharma (Shanghai) Co., Ltd. (select “protocol-defined special event” in the column of severity criteria), and fax it to the sponsor within 24 hours.

7.3.4 Recording and reporting of abnormal laboratory examinations

All the results from laboratory examinations could be recorded on the laboratory examination page in CRF/eCRF.

Any treatment-emergent sudden abnormal laboratory result should be recorded as one diagnosis on the AE page of CRF/eCRF when it is clinically significant and for example, meets at least one of the following conditions:

- ◆ with clinical symptoms;
- ◆ leading to change of study drug (eg., dose adjustment, interruption or permanent discontinuation);
- ◆ requiring to change the concomitant therapy (eg., concomitant medication, addition of treatment or management, interruption, discontinuation or other changes)

This is applicable for the results of laboratory examinations for safety and efficacy described in or out of any protocol after the first dose, if they are out of the reference range and meet the criteria on clinical significance.

This is not applicable for the results of laboratory examinations that are out of the reference range but don't meet the criteria on clinical significance (only analyzed and reported as laboratory abnormality).

Please note: any abnormal laboratory result should be reported as SAE if it meets the criteria on SAE, and recorded as AE in the CRF/eCRF.

The procedure for all the AE/SAE reporting is provided in Appendix 3.

7.4 Follow-up of subject

7.4.1 Follow-up of Adverse Event(s)

The investigator should follow up all the AEs, until occurrence of any of the following conditions:

- AE is relieved or improved to baseline level;
- No further improvement is expected, as confirmed by the investigator;
- Subject dies;
- loss of contact with the subject;
- no correlation between the AE and investigational therapy, as confirmed by the investigator;
- start of new anticancer therapy;
- No more collection of clinical or safety data, or final closure of database.

The final outcome of each AE (including the date when AE is relieved or the subject dies) must be recorded in the CRF/eCRF.

7.4.2 Follow-up of Serious Adverse Event(s)

All the SAEs should be followed up as much as possible, until they are relieved or improved to baseline level, subject's death, loss of contact or the investigator finally confirms the SAE is unrelated with the investigational therapy. The investigator should fill the follow-up information of SAE as the follow-up report or summary report in the Serious Adverse Event Report Form, meanwhile fill in the SAE Report Form of Clinical Studies provided by the sponsor, and report it in accordance with the expedited reporting procedure for serious adverse event (as shown in 7.3.2).

The sponsor could obtain more information about the event from the investigators via telephone, email, fax or monitoring visit for part of the SAEs.

7.4.3 Follow-up of protocol-defined special events

In addition to the routine follow-up of SAE, all the protocol-defined special events need to be followed up in accordance with the Clinical Assessment of Hepatic Impairment provided in Appendix 4 of the clinical study protocol, as to obtain more valid information for evaluation of this event.

7.4.4 Follow-up of abnormal laboratory results

The test should be performed again and followed up for any abnormal laboratory results with medical significance but unclear explanation until it is recovered to normal, baseline and/or adequate explanation is found. The clear explanation should be recorded on the CRF/eCRF if it is available.

7.5 *Pregnancy and management of pregnancy*

Female subjects must be informed that any pregnancy during the study must be reported to the investigator immediately, and the study drug must be discontinued. Any pregnancy within 30 days after the end of therapy should also be reported to the investigators.

The pregnancy itself is not an adverse event, unless it could affect and interfere with the efficacy of contraceptive agent. However, once pregnancy occurs, the investigator must report it to the sponsor within 24 hours after awareness of the event. At the same time, the investigator should sincerely advise the subject and discuss with her the risk of continuous pregnancy as well as the potential effect on the fetus. The pregnancy in the female partner of male subject during the study needs to be reported as well. In summary, the partner of a subject should be also advised sincerely and followed up.

The event of pregnancy should be followed up until the end of pregnancy. Outcome of all the pregnancies (spontaneous abortion, artificial termination of pregnancy, normal birth or congenital abnormality) must be followed up and recorded, even though the subject

has withdrawn from the study. Outcome of all the pregnancies must be reported through pregnancy outcome form.

All congenital abnormalities and birth defects are SAEs. Abortion should be reported as SAE regardless of therapeutic or spontaneous abortion (important medical event).

8 Statistics and analysis plan

8.1 Primary and secondary research variables

Primary variables:

Overall incidence of adverse events

Incidence of Grade 3/4 adverse events

Incidence of serious adverse events

Incidence of adverse events leading to permanent discontinuation

Incidence of adverse events leading to interruption/reduced dose

16-week progression-free survival rate

Secondary variable:

Effectiveness:

"Event occurrence date" variable: Calculated since the day when the informed consent is signed. If no event is observed, there is no date of end, and a so called cutoff observation has to be considered for analysis. The cutoff date is: The last date, such as for "last tumor measurement", "last medication registration", or "last visit".

Secondary efficacy variables include objective response rate, disease control rate, duration of response, progression-free survival, and overall survival.

Objective response rate (ORR): defined as the incidence of confirmed complete response (CR) or partial response (PR), the target lesions and non-target lesions are evaluated with validated radiological method and judged in accordance with RECIST criteria 1.1.

Progression-free survival (PFS): defined as the time from the signature of informed consent form to the first recording of progression of disease (PD) or date of death, whichever comes first. If no PD is observed, the censoring date should be the date of the last tumor measurement.

Overall survival (OS): defined as the time from the signature of informed consent form to date of death for any reason. If no death is observed, the last follow-up date is regarded as the censoring date.

Disease control rate (DCR): defined as the incidence of confirmed complete response (CR), partial response (PR) and stable disease (SD), the target lesions and non-target lesions are

evaluated with validated radiological method and judged in accordance with RECIST criteria 1.1.

Duration of response: defined as the time from the first recording of CR or PR to the first finding of PD for patients who have achieved response. For those with no record of PD after CR or PR, the censoring date is the date of the last tumor measurement.

Safety and Tolerability:

Safety and tolerability of the treatment are evaluated by incidence and severity of adverse events, laboratory tests, vital signs, ECG, LVEF, and ECOG performance status.

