Information on subsequent treatment												X
Survival:											X	X

Notes:

- The baseline tumor assessment will be done within 2-3 weeks prior to administration, four sites (neck, chest, abdomen and pelvis) are evaluated in accordance with

RECIST1.1 criteria. Using the radiological (CT/MRI) examination, the baseline evaluation and post-treatment efficacy evaluation are performed with the same method and by the same investigator; tumor radiological assessment (CT or MRI) is performed every two cycles of treatment (8 weeks), until progression of disease. If the tumor is assessed as complete response or partial response (CR or PR), it needs to be re-confirmed 4 weeks later. If the subject receives the drug for less than 56 days, tumor assessment could be performed at the end of medication when necessary, according to investigator's judgement.

2. The vital signs include blood pressure, heart rate, respiratory frequency and temperature, and are monitored 2 hours(\pm 1 hour) after administration;
3. Hematological examination: red blood cell, hemoglobin, platelet count, neutrophil and its differential categories; prothrombin time (PT), activated partial thromboplastin time(APTT), thrombin time(TT), fibrinogen quantification(FIB) and INR. If the neutrophil is $\leq 1 \times 10^9/L$ or platelet count is $\leq 25 \times 10^9/L$, the frequency of repeated testing needs to be increased (once/2-3 days);
4. Serum chemistry: if 3 times elevation of ALT or AST occur during the trial, the frequency of repeated testing needs to be increased (2-3 times/week advised); the creatinine clearance at baseline is calculated based on the creatinine level (formula: $Ccr = (140 - \text{age}) \times \text{body weight}(\text{kg}) / [72 \times \text{Scr}(\text{mg/dl})]$ or $Ccr = [(140 - \text{age}) \times \text{body weight}(\text{kg})] / [0.818 \times \text{Scr}(\text{umol/L})]$, the unit of creatinine should be noted during the calculation of creatinine clearance, the result for female is the calculated result $\times 0.85$);
5. Routine urinalysis is used for measurement of urine protein, and needs to be repeated when urine protein ++ occurs once, 24-hour urine protein quantification is required for urine protein++ in consecutive two measurements;
6. 12-lead ECG is performed in screening period, 4 hours(\pm 1 hour) after administration on Day 7, 14, 21 and 28; and by the frequency of follow-up from the 2nd cycle of therapy;

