6.2 Clinical Assessment

6.2.1 Effectiveness

6.2.1.1 Effectiveness endpoint

All the effectiveness endpoints in the randomized comparison study are secondary endpoints.

Secondary endpoints:

Objective response rate (ORR) determined in accordance with RECIST1.1

Disease control rate (CR+PR+SD), where SD \geq 8 weeks

Duration of response

Progression-free survival (PFS)

Overall survival (OS)

Primary effectiveness endpoint in the expansion part is the progression-free survival at Week 16

The secondary endpoints are DCR, ORR and OS

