6.2.1.2 Assessment of effectiveness

The tumor is evaluated in accordance with RECIST1.1 criteria, and the detailed evaluation criteria are provided in Appendix 2. The radiological evaluation of tumors could use CT or MRI as decided by investigators, however, the apparatus and technical parameters should keep consistent throughout the study; contrast agent should be used in case of no contraindications. If the tumor evaluation has been performed 14-21 days before the first dose, and the same method and apparatus are used in the same hospital, this evaluation could be used as the baseline tumor evaluation. The baseline tumor evaluation should include neck, chest, abdomen, pelvis and any other sites that are suspected to have tumor lesions. Bone scan should be used for follow-up of the disease in patients with bone metastasis.

Record of target lesions: number, site and description of lesions, the maximum diameter measured for each lesion (except lymph node) and the minimum diameter measured for lymph node, sum of diameters including all the target lesions;

Subjects will receive the first tumor evaluation after 2 cycles of treatment, and one evaluation every two cycles subsequently, until progression of disease. If complete response or partial response occurs, it needs to be confirmed after 4 weeks. If the patient interrupts the dose for adverse drug reaction or other reasons, the tumor evaluation will be performed once every 8 weeks as originally scheduled. If the patient discontinues the study drug within 56 days, the tumor evaluation should be performed as early as possible after discontinuation of the drug.

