8.2.2 Statistical Methods

Efficacy Analysis:

Randomized comparison part-secondary efficacy endpoint analysis:

The inter-group difference of objective response rate is compared by CMH Chi-square test.

Secondary efficacy endpoint analysis: Descriptive statistical analysis.

Progression-free survival is analyzed by Kaplan-Meier method;

Overall survival is analyzed by Kaplan-Meier method;

The inter-group difference of disease control rate is compared by CMH Chi-square test;

The duration of response is analyzed by Kaplan-Meier method; the median time to response and its 95% confidence interval are listed for the two groups.

Expansion part- primary efficacy endpoint analysis:

The 16-week progression-free survival rate is calculated in patients with advanced colorectal cancer who have failed with standard care and are receiving drug administration of 5 mg qd 3-week on/1-week off in the study. Secondary endpoints are analyzed by descriptive statistical analysis.

At the end of the trial, the survival (including median survival and 9-month survival rate) in patients with advanced colorectal cancer who have failed with standard care and are receiving drug administration of 5 mg qd 3-week on/1-week off is analyzed.

Safety analysis:

Safety analysis population: The safety analysis population includes the patients signing the informed consent who receive at least one dose of the treatment.

All safety parameters are summarized, and are tabulated by the safety population.

The frequency table (overall and by intensity) of adverse events is listed by system organ class. In the table of the overall incidence of adverse event, subjects with the same adverse event more than once is only counted once in the frequency table.

Shift table and frequency table are used simultaneously for summary of laboratory data according to sampling timepoint.

All the AEs and abnormal laboratory variables are evaluated according to CTCAE v4.0 grading system.

ECOG performance status will be summarized by descriptive statistics. Vital signs, ECG, and echocardiography will be described by tabulation.

During the randomized comparison part, inter-group differences are compared by CMH Chi-square test, based on the primary safety endpoints.

The overall incidence of adverse events, incidence of G3/4 adverse events, and severe adverse events are compared between the two groups;

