4.6.3. Stable Disease Period

The stable disease period is the period from the start of treatment (from randomization time in randomized trials) to progression of disease; the minimum sum during the trial is used for reference (if the sum at baseline is minimum, then it is used for reference for calculation). The clinical relevance during stable disease period varies in different studies and for different diseases. If, in a certain trial, the proportion of patients maintaining the minimum stable disease time is used as study endpoint, then the protocol shall describe particularly the minimum time interval between two measurements in the definition of SD.

Notes: The response period and the stable disease period are impacted by follow-up frequency after baseline evaluation. To define a standard follow-up frequency, it does not fall in the range of this Guideline. Multiple factors should be considered for follow-up frequency, such as disease type and stage, treatment cycle, and standard specification, etc. If it requires a comparison between trials, restrictions for accuracy of those measurement endpoints should be taken into account.

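### Timing PFS from informed consent while scans run from first dose pushes most Week-16 scan progressions past Day 112, biasing the expansion part's primary 16-week PFS rate upward toward the 8-week rate

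*Protocol*

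**What the plan says.** Section 6.2.1.1 sets the endpoint: "Primary effectiveness endpoint in the expansion part is the progression-free survival at Week 16". Section 8.1 lists the 16-week PFS rate among the primary variables, and Section 8.2.2 says only that "The 16-week progression-free survival rate is calculated in patients with advanced colorectal cancer" on the expansion regimen.

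The clock is in Section 8.1. Event-date variables are "Calculated since the day when the informed consent is signed", and PFS is "defined as the time from the signature of informed consent form to the first recording of progression of disease (PD", or to death if earlier.

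The scans run on another clock. Section 6.2.1.2: "Subjects will receive the first tumor evaluation after 2 cycles of treatment, and one evaluation every two cycles subsequently, until progression of disease". Note 1 to the study flowchart (Section 6) gives the interval: "tumor radiological assessment (CT or MRI) is performed every two cycles of treatment (8 weeks), until progression of disease". Section 3.1.1 fixes a cycle at 28 days, so the second scan is due at treatment Day 112.

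Section 6.1 requires consent before any study-specific procedure, and the flowchart's screening column opens at Day -14. The protocol states no other time zero for the 16-week rate, no window around the Week-16 scan and no rule assigning scans to nominal weeks. Appendix 2, Section 4.6.3, uses a different origin for a related quantity: "The stable disease period is the period from the start of treatment (from randomization time in randomized trials) to progression of disease".

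**The concern.** The landmark (112 days) coincides with a scheduled scan only if time is counted from first dose. Counted from consent, that scan moves beyond the landmark by the consent-to-dose lag. A patient who progressed between Weeks 8 and 16 and was found at the Week-16 scan then has a recorded PFS above 112 days and counts as progression-free at 16 weeks. For most patients the only routine scan that can produce an event by the landmark is the one at Week 8.

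This affects the primary efficacy estimate of a single-arm part. No concurrent control shares the error, so the rate would look better than a 16-week rate timed from treatment start. An SAP that follows Section 8.1 and reads the rate at 112 days would reproduce the bias.

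**Working it through.** The protocol gives no target or null rate for 16-week PFS, so there is no stated figure to reproduce. The check is date arithmetic, then an illustrative model.

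**Inputs from the protocol.** Consent origin (8.1); scans at treatment Days 56 and 112 (3.1.1, 6.2.1.2, flowchart note 1); Day 56 window ±2 days (flowchart); median PFS 3.7 months, the interim figure for the 3/1 group (3.1.2).

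**Assumptions.**
- The Day 112 window is ±3 days, as printed for Day 84; none is printed for Day 112.
- The lag L from consent to first dose is 1 to 14 days (flowchart screening) or up to 21 days (baseline scan 2 to 3 weeks before dosing, if consent precedes it). A short lag of 0 to 3 days was also run.
- PFS is exponential from first dose. A share d of events (deaths, for example) is seen at once; the rest are dated at the detecting scan.
- The rate is read at 112 days on the Section 8.1 clock.

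**Step 1: dates.** Scan day on the PFS clock = treatment day + L. The Week-16 scan falls on:
- L = 1: Days 110–116; 3 of 7 window days are by Day 112.
- L = 3: Days 112–118; 1 of 7.
- L = 7: Days 116–122; none.
- L = 14: Days 123–129; none.
- L = 21: Days 130–136; none.

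The earliest permitted scan is Day 109 + L, which exceeds 112 whenever L ≥ 4. The Week-8 scan (Days 54–79 for L from 0 to 21) always counts.

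**Step 2: size at a median of 3.7 months.** The median is 3.7 × 30.4375 = 112.6 days.
- S(56) = 2^(−56/112.6) = 0.708
- S(112) = 2^(−112/112.6) = 0.502

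If p is the share of Week-16 scans dated by Day 112, then approximately:

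rate read = (1 − d) × [S(56) − p × (S(56) − S(112))] + d × S(112 − L)

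- L uniform on 1–14: p = (3/7 + 2/7 + 1/7)/14 = 0.061, so about 94% of these scans are late. With d = 0 the rate is 0.708 − 0.061 × 0.206 = 0.695.
- Same lag, d = 0.25, mean L = 7.5: S(104.5) = 0.526, giving 0.75 × 0.695 + 0.25 × 0.526 = 0.653.
- L uniform on 0–3: p = (4/7 + 3/7 + 2/7 + 1/7)/4 = 0.357, giving 0.708 − 0.357 × 0.206 = 0.634.

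Simulation with 400,000 patients per scenario gives 0.695, 0.652 and 0.637.

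**Step 3: range.** Simulated rates in %, over d = 0 to 25%; the main lag column covers lags of 1–14, 7–14 and 14–21 days. Excess is in percentage points over the true 16-week rate.

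| Median (months) | True 8-wk | True 16-wk | Read, lag 1–21 d | Excess | Read, lag 0–3 d | Excess |
|---|---|---|---|---|---|---|
| 2 | 52.9 | 27.9 | 46.2–52.8 | 18.3–24.9 | 40.2–44.2 | 12.3–16.3 |
| 3 | 65.4 | 42.7 | 59.3–65.4 | 16.6–22.7 | 53.9–57.4 | 11.2–14.7 |
| 3.7 | 70.8 | 50.2 | 65.2–70.9 | 15.0–20.7 | 60.4–63.7 | 10.2–13.5 |
| 5 | 77.5 | 60.0 | 72.9–77.5 | 12.9–17.5 | 68.7–71.4 | 8.7–11.4 |
| 6 | 80.9 | 65.4 | 76.8–80.9 | 11.4–15.5 | 73.0–75.6 | 7.6–10.2 |

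**Step 4: does a new origin suffice?** With first dose as time zero and an exact Day 112 cut, 3 of 7 window days are still late (p = 4/7): 0.708 − 0.571 × 0.206 = 0.590, and the simulation gives 0.593. Counting through Day 115 gives 0.501, and reading at Week 17 (Day 119) gives 0.502, both matching the true 0.502 to rounding.

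**The case against.** **The cut is assumed.** No section says the rate is read at exactly 112 days from consent. The endpoint is worded as PFS at Week 16, flowchart days count from dosing, and the consent-origin text stands under the secondary variables. A nominal-visit reading is possible, and visit-window rules are ordinary SAP content. This stands in part: a missing window alone would be no finding. But Section 8.1 gives the only PFS definition and fixes consent as its origin, and the 16-week rate has no other.

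**The size is soft.** The screening header is partly garbled in the text at hand, the Day 112 window is borrowed, and deaths count when they occur. The 3.7 months is an observed interim median, presumably scan-detected already, used here as a latent one. All of this stands, so the size is given as a range and the 3.7-month row is only an illustration.

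**Stronger readings that a reader might infer.**
- That every Week-16 progression is lost and the endpoint simply is an 8-week rate. Short lags let some Week-16 scans count, and deaths and off-schedule progressions before Day 112 still count.
- That the disease control rate is defined inconsistently. Section 8.1 omits the 8-week stable-disease minimum of 6.2.1.1 but does not contradict it. A first scan permitted on Day 54 is a two-day visit-window matter.
- That Appendix 2 contradicts Section 8.1. Section 4.6.3 there defines the stable-disease period, not PFS.
- That the choice of regimen was distorted. It was made from the randomized part before expansion, and both arms there share the same origin.

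**The stakes are limited.** The expansion part has about 20 patients and no success threshold; an exact 95% interval for 10 of 20 is 27 to 73%. That argues for proportion. It does not excuse a bias that a change of wording removes.

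**Conclusion.** The point holds. Under Section 8.1 as written, read at 112 days, most progressions first seen at the Week-16 scan are dated after Week 16. With a lag of 4 days or more and a ±3-day window, that is true of all on-schedule ones. The direction of the bias follows from the protocol's own definitions. Its size rests on the stated assumptions: about 11 to 25 percentage points for lags of 1 to 21 days, and about 8 to 16 for lags of 0 to 3 days. In a group of 20, a shift from 50% to 70% is 4 patients.

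Overall survival and the 9-month survival rate also include the time from consent to first dose. That is a minor consequence of the same origin.

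**What to change.** In Section 8.1, set time zero for PFS and overall survival to first dose in the expansion part and to randomization in the randomized part.

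Define 16-week PFS as alive without progression through the scheduled second on-treatment scan, including its visit window; for example, a Kaplan-Meier estimate read at Week 17 from first dose. State the Day 112 window so that the reading time covers it. Both changes are needed: first dose with an exact Day 112 cut still reads about 59% where the true rate is 50%.

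The cost is wording only; consent, dosing, randomization and scan dates need no new collection. The reported 16-week PFS rate will be lower.
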